
In the second step of recruitment, consented Veterans who have completed baseline testing, are diagnosed with OSA (based on sleep clinic physicians interpretation of sleep study results) and are prescribed PAP therapy (by sleep clinic clinicians) will be reminded of study procedures, and invited to participate in the randomized controlled trial. Inclusion criteria will include: 1) age \geq 50 years, 2) meeting ICSD2 diagnostic criteria for insomnia, and 3) diagnosis of OSA with an AHI \geq 15 and prescription of PAP therapy. Exclusion criteria for randomization will include the following: 1) refusal to schedule an appointment to begin PAP therapy, 2) a Mini-mental State Examination (MMSE) score < 24 (used to screen for significant cognitive impairment), and 3) a history of mania (which is a contraindication for the sleep restriction component of CBT-I), major psychopathology (e.g., psychosis) or a psychiatric hospitalization within the prior two years.

- Randomization

Participants will be randomized to the intervention or control group using a randomized block design based on results from the OSA testing, to increase the likelihood of comparable severity of OSA in both groups. Specifically, individuals will be categorized based on AHI < 30 or AHI \geq 30. Consented participants will be randomized as a block within each category (similar to block randomization techniques we have used in prior research). Available randomization software (e.g., Random Allocation Software, Paradigm) which allows for block randomized sequences for parallel group randomized trials will be used to assign participants to the intervention or control group, using random allocation concealment. Participants and research staff (except intervention staff) will be blinded to group assignment, and additional techniques (e.g., follow-up assessment in some consented, non-randomized participants) will be used to prevent unmasking. It may be difficult to keep assessment research staff blinded to group assignment if participants inadvertently describe their assignment, but all assessment staff will also be blinded to study research questions.

Dependent and Independent Variables (Measurement Techniques)

A summary of all measurement techniques is shown in Table 1.

Baseline Assessment

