The analysis plan for each specific hypothesis is listed below. In addition to hypothesis testing to analyze effects of the intervention on sleep, PAP adherence, depressive symptoms and quality of life, we will develop models showing which covariates predict the values of each of the outcome measures. Prior to hypothesis testing, data will be cleaned, possible outliers identified, and data distributions evaluated for assumptions of analysis (e.g. normality, homogeneity of variance). If necessary, normalized rank transformations as described in Bonate²⁴ will be performed and normalized rank scores will be submitted to analysis.

Hypothesis 1: Compared to control participants, participants randomized to the intervention will have improved nighttime sleep (i.e., higher sleep efficiency, better self-reported sleep) and better PAP adherence (measured objectively) at 3-months follow-up.

This hypothesis tests for differences between the intervention and control groups in our primary outcome measures of nighttime sleep and PAP adherence, between baseline assessment and 3-months follow-up, which is our primary time endpoint. Subjective measures of sleep outcomes will include sleep diary (sleep onset latency, wake after sleep onset [WASO], and sleep efficiency) and sleep quality (PSQI). The objective measure of sleep outcome will be actigraphy (sleep efficiency), and the objective measure of PAP adherence will be downloaded from the PAP smart card (percent of nights with PAP use \geq 4 hours, and mean hours of PAP use per night). All outcomes will be assessed using intention to treat analyses. A 2 X 2 (time X group; where time = baseline or 3-month assessment; and group = intervention or control) analysis of covariance analysis will be used with Bonferroni-corrected post-hoc comparisons to investigate differences between the groups in terms of treatment effects in the sleep variables (where baseline and 3-month follow-up data will be available). For PAP adherence outcomes, there will be no “baseline” data (i.e., PAP adherence data isn’t available until the participant starts PAP therapy), so outcomes between groups will be compared with independent samples t-tests and Chi-square test for difference in proportions.

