We expect that the group by time analysis of covariance for the sleep variables will show a difference between groups, and post-hoc analyses will show increased nighttime sleep efficiency and improved self-reported sleep (indicated by lower PSQI scores) in the intervention group compared to the control group. Following review of graphical representation of our longitudinal results (on main outcome measures), we will use repeated measures ANCOVA models to test both linear and nonlinear (i.e., quadratic) differential changes over time. Post-hoc tests within each time point (using Tukey type 1 error control) will be conducted. We expect there will be no difference between intervention and control groups at baseline, but differences will be present at follow-up. Other participant characteristics will be considered as possible covariates to reduce bias in our estimate of treatment effects and to increase precision. The major covariates that we expect to consider are age, cognition (estimated by MMSE) and comorbidity (estimated by CIRS-G). Other covariates we will consider include specific diagnoses and medications that may interfere with sleep, and measures of the intervention process (DBAS-16 scores, Self-efficacy, Knowledge and Decisional Balance Index subscales).

Sample size calculations were performed for each of the main outcome variables using reported effect sizes and/or calculated effect sizes from reported sample means and standard deviations reported in the literature in prior studies of CBT-I for insomnia and behavioral PAP adherence interventions in outpatient adults (see Table 5). Prior literature indicates that CBT-I is an extremely potent intervention for insomnia, and the studies typically have large effect sizes and small samples. Some caution is warranted, however, since efficacy studies usually employ tightly controlled ‘ideal’ treatment conditions, which also yield larger effect sizes

than effectiveness studies with more ‘real world’ conditions. Regardless of these issues, even the most conservative estimates of effect size from the literature suggest we will have an adequate sample size to test our sleep outcomes. A recent meta-analysis of trials of PAP adherence interventions published as a Cochrane review was used in estimating sample size for the PAP adherence component of our intervention.^{Error! Bookmark not defined.} this analysis suggests we will have an adequate sample size to test our PAP adherence outcomes.

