For the proposed study, we calculated sample size based on the outcome at post-treatment, and either the reported effect size (d) or d calculated from the reported means and SDs. The table below lists sample size needs for the entire duration of the study (i.e., 6 months). Based on an expected 15% loss by six months, the 5th column in the table below projects the sample size needed for each of 2 groups at randomization to maintain sufficient sample size at 6 months to test the selected outcomes.

Table 5 lists expected effect size, shown as the variable “d” (difference between intervention and control groups at follow-up divided by standard deviation). For many outcomes, we list several expected effect sizes from the literature; references for these effect sizes are listed in the second column. The effect size estimates take into account expected change in controls over time, since we expect controls will change, but not as much as the intervention group. The sample size needed at randomization to detect effect size d is shown (column 4), followed by the number of enrolled participants needed for the 6-month analyses (column 5), taking into account expected dropout by this time point. Based on these calculations, 120 randomized participants (60 per group) will be adequate for analyses at both 3 and 6 months. In addition to these main analyses, we will perform follow-up subgroup analysis to identify two or three variables which identify participants who have the greatest positive response to the intervention. Testing for subgroups with better or worse response results in such a small sample that overfitting is a potential problem; this risk is discussed below.

For example, in Table 5 the third row (WASO by sleep diary) shows that to have the needed sample size (N=19 per group) completing the study (i.e., with follow-up assessment data) to test for an effect (based on an expected 15% participant loss by 6 months), we need to enroll 22 participants per group (column 5) at baseline to have 19 participants per group remaining at 6 months follow-up. For all variables listed, we expect an adequate sample size to test our hypotheses. For all sample size calculations, the dropouts are assumed not to change on average. All testing assumes a two-sided .05 significance level with 80% power.

Table 5: Sample size calculations

Outcome	Reference	Reported (or calculated) effect size d	Enroll per group for d: post-test	Enroll per group for d at 6 months
WASO				

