There are statistical problems we may encounter in analyses, including the statistical handling of participant dropout, possible differential treatment effects across randomization blocks, and the risk of overfitting the data. To deal with dropouts, we will use standard "intention to treat" analysis. The main independent variable will be whether a participant is in the intervention or control group, rather than whether the participant actually receives the intervention. If the participant rejects the intervention at some point after randomization, but allows us to collect follow-up data, we will use standard "intention to treat" analysis. If the participant stops providing data, we will do analyses using all available data, and then repeat analyses after estimating missing data using an EM (expectation-maximization) algorithm, which is less subject to bias than other methods such as carrying forward the last available value; results from both analyses will be reported. It is important to address dropouts, since those who complete the study may be more compliant or healthier than those who drop out. To understand how "completers" may differ from "dropouts", we will compare their baseline characteristics. Dropout rates and characteristics of dropouts will also be compared between groups.

To address the risk of a differential effect of the intervention between randomization blocks, we will test for a block by group interaction. If one is present (suggesting the treatment is more or less effective for one stratification group over another), the results cannot be pooled, which impacts statistical power. However, we anticipate overall treatment effect will overshadow any differential effects across stratification blocks.

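### A block by group interaction should not stop pooling: keep the AHI-stratum-adjusted overall effect primary and put the stratum in every main model

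*Combined protocol and SAP*

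**What the plan says.** Under Randomization, the plan states: "Participants will be randomized to the intervention or control group using a randomized block design based on results from the OSA testing". The two categories are AHI below 30 and AHI 30 or more.

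Under Analysis Plan and Hypotheses (Hypothesis 1), sleep outcomes are analysed by a time by group analysis of covariance. For PAP adherence, "outcomes between groups will be compared with independent samples t-tests and Chi-square test for difference in proportions". On covariates for the sleep models: "The major covariates that we expect to consider are age, cognition (estimated by MMSE) and comorbidity (estimated by CIRS-G"). The same paragraph leaves others open: "Other participant characteristics will be considered as possible covariates to reduce bias in our estimate of treatment effects and to increase precision". The AHI stratum is not named.

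Under Potential Shortcomings in the Proposed Analysis, a block by group interaction test is planned, with this consequence: "If one is present (suggesting the treatment is more or less effective for one stratification group over another), the results cannot be pooled". The sentence goes on to concede an effect on power, without giving its size. The next sentence reads: "However, we anticipate overall treatment effect will overshadow any differential effects across stratification blocks". No significance level is given for the interaction test. Nor is there error control for separate stratum analyses, or a statement that the overall effect stays primary.

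The sample size text concludes: "Based on these calculations, 120 randomized participants (60 per group) will be adequate for analyses at both 3 and 6 months".

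**The concern.** The condition for not pooling is any difference in the size of benefit between strata, not only a reversal of direction. A difference in size does not invalidate the overall comparison. Treatment is randomized within each stratum, so the stratum-adjusted difference estimates an average effect over the enrolled population. An interaction bears on how that average is read, not on whether it may be reported.

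Under the plan's wording, a preliminary test chooses the main result after the data are seen. Three things are at stake:

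- The sample size was justified for the pooled comparison. Half-size strata do not have that power.
- A chance interaction under a uniform benefit would usually turn one clear result into an apparent benefit in one severity group only.
- If a win in either stratum then counts as success, type I error exceeds 5%.

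A smaller point is that the stratum used to randomize is missing from the main analyses. A t-test and an unstratified chi-square cannot carry it. Those tests remain valid, and they lose precision only if AHI group predicts the outcome.

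**Working it through.** **Inputs from the documents.** Two-sided .05 and 80% power ("All testing assumes a two-sided .05 significance level with 80% power"); 60 per group randomized; 15% loss by 6 months, leaving 51 per group (Sample size estimates); PAP adherence d=.59, 47 per group at post-test (Table 5).

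**Assumptions.** Interaction test at .05; AHI split 25/26 per arm (even) or 15/36 per arm (30/70); normal outcomes with SD 1.

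**1. The plan's own figure.** n per group = 2(1.960 + 0.842)² / 0.59² = 45.1, so 46 by the normal formula and 47 with the t distribution. Table 5's 47 reproduces.

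**2. Power, pooled and by stratum (d=.59, t-based).**

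| Comparison | n per arm | Power |
|---|---|---|
| Pooled | 51 | 84% |
| Even split | 25 / 26 | 53% / 55% |
| 30/70 split | 15 / 36 | 35% / 69% |

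For 80% power in each of two equal strata, 4 × 47 = 188 completers are needed. At 15% loss that is 47/0.85 = 55.3, so 56 per cell and 4 × 56 = 224 randomized, against 120 planned.

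**3. The interaction test as a gate.** In SD units the standard error of the difference between stratum effects is √(2/n₁ + 2/n₂).

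- 25/26: √(2/25 + 2/26) = 0.396; 80% power needs a difference of 1.12 SD (noncentral t, 98 df).
- 15/36: √(2/15 + 2/36) = 0.435; 80% power needs 1.23 SD.
- A true difference of 0.4 SD is detected 17% of the time (25/26).

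With no true interaction the gate fires in 5% of trials per outcome. Hypothesis 1 has seven measures: diary sleep onset latency, WASO and sleep efficiency; PSQI; actigraphy sleep efficiency; percent of nights; and mean hours of PAP use. If they were independent, the chance of at least one false trigger would be 1 − 0.95⁷ = 30%. Correlation would lower this.

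**4. Simulating the rule** (60,000 trials per scenario; 120,000 under the null).

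| True effects by stratum | Split | Rule fires | Pooled test significant | Significant and still poolable |
|---|---|---|---|---|
| .59 / .59 | 25/26 | 5% | 84% | 80% |
| .59 / .59 | 15/36 | 5% | 84% | 80% |
| about .79 / .39 | 25/26 | 17% | 84% | 69% |
| about .90 / .30 | 25/26 | 32% | 83% | 57% |

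Under the uniform effect, exactly one stratum is significant in 96% of triggered trials (88% with 15/36).

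**5. What counts as success after a trigger.** The plan does not say, and the consequence depends on it.

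- Either stratum counts: type I error is about 8% (7.9% for both splits), and power at d=.59 is about 85%, so no power is lost.
- Both strata must be significant: type I error is about 5%, and power is about 80%.

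**6. Leaving the stratum out (25/26, d=.59).**

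| Stratum effect on outcome | Power adjusted | Power unadjusted | Unadjusted type I error |
|---|---|---|---|
| 0 SD | 84% | 84% | 5% |
| 0.5 SD | 84% | 82% | 4.5% |
| 0.8 SD | 84% | 80% | 3.4% |
| 1.0 SD | 84% | 78% | 2.9% |

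Omission makes the test conservative; it does not inflate error.

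**The case against.** The strongest reply has five parts.

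- **The harms do not add.** Lost power and inflated error belong to different success rules, as step 5 shows. This is correct: each figure must be read under its own rule. The plan states neither rule, so one of the two problems applies but not both.
- **The chance event is rare.** The 96% is conditional on a 5% trigger, so a uniform benefit is misread in about 5% of trials per outcome. This is also correct. With unequal benefit the rule fires more often. The interaction is then real, and one stratum is usually significant, so the trial is not left without a result. It does lose its overall result, although the average effect is still valid.
- **The passage is a contingency that concedes the power cost.** It stands under potential shortcomings, and the main analysis is described elsewhere as the overall comparison. The concession does not withdraw the rule, and neither does the expectation that the overall effect will dominate.
- **Table 5 asks for only 10 to 20 per group in seven of its eight sleep rows**, fewer than an even stratum would hold. By the plan's figures those outcomes would survive a split, so the power argument rests mainly on PAP adherence. Most of those rows do not follow from a two-sample formula, however: actigraphy at d=.60 gives 45 per group, not 27. Also, 51 per arm is the 6-month number, and the primary time point is 3 months.
- **Adjustment is a matter of precision.** True, and its value depends on an AHI effect that the documents do not give. Leaving covariates open for consideration is still not pre-specification.

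**Conclusion.** The concern holds. Refusing to pool whenever a block by group interaction is present is wrong as a rule, and nothing else in the plan corrects it. That conclusion needs no assumption about sizes.

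The size depends on the interaction level, the AHI split and the success rule, none of which is stated. Under a uniform effect the power cost is modest, about 4 points. The more serious consequences are a misleading single-stratum claim when the rule fires, and the loss of the overall result when benefits differ by ordinary amounts. An undefined success rule also allows about 8% type I error. Omitting the stratum is secondary: it costs nothing if AHI group is not prognostic, and about 5 to 6 points of power at 1.0 SD. The change should be made; the trial's validity does not hang on it.

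**What to change.** In Potential Shortcomings in the Proposed Analysis, delete the statement that results cannot be pooled. Replace it with wording such as: *The pooled stratum-adjusted intention-to-treat effect is the primary result whatever the interaction test shows. The block by group interaction is exploratory and is reported with stratum-specific estimates and 95% intervals. If the stratum effects point in opposite directions, this is discussed as a limit on how the pooled effect is interpreted.*

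In Analysis Plan and Hypotheses, pre-specify the AHI stratum (<30, ≥30) in every main model:

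- Percent of nights with PAP use of at least 4 hours, and mean hours of use: linear model on arm and stratum, in place of the t-test.
- Adequate adherence (yes/no): Cochran-Mantel-Haenszel or logistic regression with stratum. Name one in advance, with its effect measure. A stratum-weighted risk difference keeps the reading as an average effect if odds ratios differ between strata.
- Sleep, mood and quality-of-life outcomes: a stratum term in each ANCOVA.

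The cost is SAP wording and one degree of freedom per model. No new data are needed, and the question of differential benefit is still answered.
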